**4.1.2.1. FIGURE: EFS BLADDER PRESERVATION VS GENDER**

#### 4.1.3. STAGE: T2 vs. T3/T4

Table 109: EFS bladder preservation by Stage: T2 vs T3/T4

T Stage	T2 (N=)	T3/T4 (N=)	Total (N=)	p value
Event Free Survival bladder preserved				
No				
Late salvage cystectomy/Bladder relapse				
Bladder relapse/Metastases				
Bladder relapse				
Metastases				
Death				
Event Free Survival bladder preserved				
Event/Death				
No				

1. Fisher's Exact Test for Count Data

Table 110: Median/mean EFS bladder preservation by Stage: T2 vs T3/T4 (estimated by Kaplan-Meier)

	Median (months)	CI 95%	Mean	CI 95%
T2				
T3/T4				

Table 111: EFS bladder preservation by Stage: T2 vs T3/T4 estimated survival ratio

EFS bladder preservation	Events (% total N)	Patients at risk	% estimated cumulative survival ratio	CI 95%
T2				
At 6 months				
At 12 months				
At 24 months				
At 36 months				
T3/T4				
At 6 months				
At 12 months				
At 24 months				
At 36 months				

**4.1.3.1. FIGURE: EFS BLADDER PRESERVATION VS STAGE: T2 VS T3/T4**

#### 4.1.4. ECOG: 0 vs. 1

Table 112: EFS bladder preservation by ECOG: 0 vs. 1

ECOG.BasDatDem	0 (N=)	1 (N=)	Total (N=)	p value
Event Free Survival bladder preserved				
No				
Late salvage cystectomy/Bladder relapse				
Bladder relapse/Metastases				
Bladder relapse				
Metastases				
Death				
Event Free Survival bladder preserved				
Event/Death				
No				

1. Fisher's Exact Test for Count Data

Table 113: Median/mean EFS bladder preservation by ECOG: 0 vs. 1 (estimated by Kaplan-Meier)

	Median (months)	CI 95%	Mean	CI 95%
0				
1				

Table 114: EFS bladder preservation by ECOG: 0 vs. 1 estimated survival ratio

Events (% total N)	Patients at risk	% estimated cumulative survival ratio	CI 95%
0			
At 6 months			
At 12 months			
At 24 months			
At 36 months			
1			
At 6 months			
At 12 months			
At 24 months			
At 36 months			

**4.1.4.1.**

**FIGURE: EFS BLADDER PRESERVATION VS ECOG: 0 vs. 1**

#### 4.1.5. Non Invasive Cancer History: Yes vs. No

Table 115: EFS bladder preservation by Non invasive Cancer History: Yes vs. No

NonInvasiveCancerHistory.BasCancer	Yes (N=)	No (N=)	Total (N=)	p value
Event Free Survival bladder preserved				
No				
Late salvage cystectomy/Bladder relapse				
Bladder relapse/Metastases				
Bladder relapse				
Metastases				
Death				
Event Free Survival bladder preserved				
Event/Death				
No				

1. Fisher's Exact Test for Count Data
2. Pearson's Chi-squared test

Table 116: Median/mean EFS bladder preservation by Non invasive Cancer History: Yes vs. No (estimated by Kaplan-Meier)

	Median (months)	CI 95%	Mean	CI 95%
Yes				
No				

Table 117: EFS bladder preservation by Non invasive Cancer History: Yes vs. No estimated survival ratio

EFS bladder preservation	Events (% total N)	Patients at risk	% estimated cumulative survival ratio	CI 95%
Yes				
At 6 months				
At 12 months				
At 24 months				
At 36 months				
No				
At 6 months				
At 12 months				
At 24 months				
At 36 months				

**4.1.5.1. FIGURE: EFS BLADDER PRESERVATION VS NON INVASIVE CANCER  
HISTORY: YES vs. No**

#### 4.1.6.PD-L1: HIGH vs. Low/NEGATIVE

Table 118: EFS bladder preservation by PD-L1: High vs. Low/Negative

PD-L1 High status	Low/Negative (N=)	High (N=)	Total (N=)	p value
Event Free Survival bladder preserved				
No				
Late salvage cystectomy/Bladder relapse				
Bladder relapse/Metastases				
Bladder relapse				
Metastases				
Death				
Event Free Survival bladder preserved				
Event/Death				
No				
1. Fisher's Exact Test for Count Data				
2. Pearson's Chi-squared test				

Table 119: Median/mean EFS bladder preservation by PD-L1: High vs. Low/Negative (estimated by Kaplan-Meier)

	Median (months)	CI 95%	Mean	CI 95%
Low/Negative				
High				

Table 120: EFS bladder preservation by PD-L1: High vs. Low/Negative estimated survival ratio

EFS bladder preservation	Events (% total N)	Patients at risk	% estimated cumulative survival ratio	CI 95%
Low/Negative				
At 6 months				
At 12 months				
At 24 months				
At 36 months				
High				
At 6 months				
At 12 months				
At 24 months				
At 36 months				

#### 4.1.6.1. FIGURE: EFS BLADDER PRESERVATION VS PD-L1: HIGH vs. Low/NEGATIVE

#### 4.1.7. CREATININE CLEARANCE: < 60 vs $\geq$ 60 (mL/min)

Table 121: EFS bladder preservation by Creatinine clearance: < 60 vs  $\geq$  60 (mL/min)

Creatinine clearance (mL/min)	< 60 (N=)	$\geq$ 60 (N=)	Total (N=)	p value
Event Free Survival bladder preserved				
No				
Late salvage cystectomy/Bladder relapse				
Bladder relapse/Metastases				
Bladder relapse				
Metastases				
Death				
Event Free Survival bladder preserved				
Event/Death				
No				
1. Fisher's Exact Test for Count Data				

Table 122: Median/mean EFS bladder preservation by Creatinine clearance: < 60 vs  $\geq$  60 (mL/min) (estimated by Kaplan-Meier)

	Median (months)	CI 95%	Mean	CI 95%
< 60				
$\geq$ 60				

Table 123: EFS bladder preservation by Creatinine clearance: < 60 vs  $\geq$  60 (mL/min) estimated survival ratio

EFS bladder preservation	Events (% total N)	Patients at risk	% estimated cumulative survival ratio	CI 95%
< 60				
At 6 months				
At 12 months				
At 24 months				
At 36 months				
$\geq$ 60				
At 6 months				
At 12 months				
At 24 months				
At 36 months				

**4.1.7.1. FIGURE: EFS BLADDER PRESERVATION VS CREATININE CLEARANCE:  
 $< 60$  vs  $\geq 60$  (mL/min)**

## 1.1. EFS BLADDER PRESERVATION UNIVARIATE AND MULTIVARIATE COX MODEL

Table 124: EFS bladder preservation univariate and multivariate Cox model

	Univariate Cox Regression				Multivariate Cox Regression				Multivariate Cox Regression (Excluding PD-L1)						
	N	Event	NHR 	95% CI 	p-value	N	Event	NHR 	95% CI 	p-value	N	Event	NHR 	95% CI 	p-value
Age at start of treatment															
Age < 71															
Age ≥ 71															
Sex															
Female															
Male															
T Stage															
T2															
T3/T4															
ECOG															
0															
1															
Non Invasive Cancer History															
Yes															
No															
PD-L1 High status															
Low/Negative															
High															
Creatinine clearance															
< 60															
≥ 60															

HR = Hazard Ratio, CI = Confidence Interval; Wald test

1.1.1.1.

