### **4.1. Inclusion criteria**

For inclusion in the study, patients should fulfill the following criteria:

1. Patients diagnosed with urothelial carcinoma of the bladder, in clinical stages T2-4a N0 M0, who are not candidates for radical cystectomy by medical reasons, refusal or patient's choice.
2. Written informed consent obtained from the patient prior to performing any protocol-related procedures, including screening evaluations
3. Age >18 years at time of study entry or Adult male or female (according to age of majority as defined as ≥18 years)

4. Patients must have ECOG performance status 0 or 1.
5. A paraffin-embedded tumor sample must be available for the associate molecular study.
6. Body weight >30 Kg.
7. Adequate normal organ and marrow function as defined below:
  - Haemoglobin  $\geq 9$  g/dL
  - Absolute neutrophil count (ANC  $\geq 1.5$  (or 1.0)  $\times$  ( $> 1500$  per mm $^3$ )
  - Platelet count  $\geq 100$  (or 75)  $\times 10^9$ /L ( $>75,000$  per mm $^3$ )
  - Serum bilirubin  $\leq 1.5 \times$  institutional upper limit of normal (ULN). This will not apply to patients with confirmed Gilbert's syndrome (persistent or recurrent hyperbilirubinemia that is predominantly unconjugated in the absence of hemolysis or hepatic pathology), who will be allowed only in consultation with their physician.
  - AST (SGOT)/ALT (SGPT)  $\leq 2.5 \times$  institutional upper limit of normal unless liver metastases are present, in which case it must be  $\leq 5$  x ULN
  - Measured creatinine clearance (CL)  $>40$  mL/min or Calculated creatinine clearance CL  $>40$  mL/min by the Cockcroft-Gault formula (Cockcroft and Gault 1976) or by 24-hour urine collection for determination of creatinine clearance:

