#### 3.18.4.1. FIGURE: CIF METASTASES AND COMPETITIVE EVENTS

## 4. PROGNOSIS FACTORS FOR EFS BLADDER PRESERVATION, EFS (SPECIFIC), PFS AND OS

### 4.1. EFS BLADDER PRESERVATION

#### 4.1.1. AGE

Table 103: EFS bladder preservation by age

Age at start of treatment	Age < 71 (N=)	Age ≥ 71 (N=)	Total (N=)	p value
Event Free Survival bladder preserved				
No				
Late salvage cystectomy/Bladder relapse				
Bladder relapse/Metastases				
Bladder relapse				
Metastases				
Death				
Event Free Survival bladder preserved				
Event/Death				
No				
1. Fisher's Exact Test for Count Data				
2. Pearson's Chi-squared test				

Table 104: Median/mean EFS bladder preservation by age (estimated by Kaplan-Meier)

	Median (months)	CI 95%	Mean	CI 95%
Age < 71				
Age ≥ 71				

Table 105: EFS bladder preservation by age estimated survival ratio

EFS bladder preservation	Events (% total N)	Patients at risk	% estimated cumulative survival ratio	CI 95%
Age < 71				
At 6 months				
At 12 months				
At 24 months				
At 36 months				
Age ≥ 71				
At 6 months				
At 12 months				
At 24 months				
At 36 months				

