**FIGURE: FOREST PLOT EFS BLADDER PRESERVATION UNIVARIATE COX MODEL**

Table 125: Creatinine clearance and ECOG contingency table, only patients with EFS bladder preservation

Creatinine clearance (mL/min)	< 60 (N=)	≥ 60 (N=)	Total (N=)	p value
ECOG				
0				
1				

1. Fisher's Exact Test for Count Data

Table 126: Creatinine clearance and ECOG contingency table, only patients without EFS bladder preservation

Creatinine clearance (mL/min)	< 60 (N=)	≥ 60 (N=)	Total (N=)	p value
ECOG				
0				
1				

1. Fisher's Exact Test for Count Data

Table 127: EFS bladder preservation multivariate model

Characteristic	Multivariate Cox Regression					Multivariate Cox Regression (Excluding PD-L1)				
	N	Event N	HR 	95% CI 	p-value	N	Event N	HR 	95% CI 	p-value
Sex										
Female										
Male										
T Stage										
T2										
T3/T4										
ECOG										
0										
1										
Non Invasive Cancer										
History										
Yes										
No										
PD-L1 High status										
Low/Negative										
High										

HR = Hazard Ratio, CI = Confidence Interval

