## 1.4. PFS

### 1.4.1. AGE

Table 152: PFS by age

Age at start of treatment	Age < 71 (N=)	Age ≥ 71 (N=)	Total (N=)	p value
Progression Free Survival (tumour assessment)				
Alive without PD				
PD (tumour assessment)				
Death				
Progression Free Survival (tumour assessment)				
PD/Death				
Alive				
1. Fisher's Exact Test for Count Data				
2. Pearson's Chi-squared test				

Table 153: Median/mean PFS by age (estimated by Kaplan-Meier)

	Median (months)	CI 95%	Mean	CI 95%
Age < 71				
Age ≥ 71				

Table 154: PFS by age estimated survival ratio

PFS	Events (% total N)	Patients at risk	% estimated cumulative survival ratio	CI 95%
Age < 71				
At 6 months				
At 12 months				
At 24 months				
At 36 months				
Age ≥ 71				
At 6 months				
At 12 months				
At 24 months				
At 36 months				

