## 1.6. OS

### 1.6.1. AGE

Table 176: OS by age

Age at start of treatment	Age < 71 (N=)	Age $\geq$ 71 (N=)	Total (N=)	p value
Status				
Alive at end of trial: Patient's decision				
Alive at end of trial according to protocol				
Death				
Patient status				
Death				
Alive				

1. Fisher's Exact Test for Count Data

Table 177: Median/mean OS by age (estimated by Kaplan-Meier)

	Median (months)	CI 95%	Mean	CI 95%
Age < 71				
Age $\geq$ 71				

Table 178: OS by age estimated survival ratio

OS	Events (% total N)	Patients at risk	% estimated cumulative survival ratio	CI 95%
Age < 71				
At 6 months				
At 12 months				
At 24 months				
At 36 months				
Age $\geq$ 71				
At 6 months				
At 12 months				
At 24 months				
At 36 months				

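### The SAP's by-factor survival tables name only count tests that ignore event time, and its seven- and six-factor Cox models are too large for 32 patients to support prognostic conclusions

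*Combined protocol and SAP*

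**What the plan says.** SAP section 4 takes four endpoints (EFS bladder preservation, EFS specific, PFS, OS) and seven binary factors: age, sex, T stage, ECOG, non-invasive cancer history, PD-L1 and creatinine clearance.

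- **Cox models.** Under "EFS BLADDER PRESERVATION UNIVARIATE AND MULTIVARIATE COX MODEL", Table 124 has univariable columns, a seven-factor model and a six-factor model without PD-L1. Tables 149, 173 and 197 repeat this for the other endpoints. For the first endpoint only, Table 127 ("EFS bladder preservation multivariate model") adds a five-factor model and a four-factor model without PD-L1. No rule is given for choosing its factors. The forest plots show the univariable results only, for example "FOREST PLOT EFS BLADDER PRESERVATION UNIVARIATE COX MODEL".
- **By-factor tables.** Seven factors times four endpoints gives 28 tables (103 to 194). Each has an event-type block (for PFS with rows such as "Alive without PD", for OS "Alive at end of trial according to protocol") above an event yes/no block, with one p-value column. All 28 footnote Fisher's "Exact Test for Count Data". Tables 103, 115, 118, 140, 152 and 164 also footnote Pearson's "Chi-squared test". No log-rank test is named in the tables or text.
- **Protocol.** Table 8 (section 11.2.2) gives Kaplan-Meier estimation, and no Cox model, for the time-to-event endpoints it lists. EFS (specific) is not among them.
- **Status.** The prognostic section has no exploratory label. Protocol 2.3 calls immune-biomarker prediction of response and bladder preservation exploratory, which reaches PD-L1 but not the other six factors.

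**The concern.** There are two separate problems.

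First, a count test on event yes/no treats an early event and a late one alike, and a patient censored at two years like one followed for nearly four. The univariable Cox Wald p-value for the same factor does use time. A reader may therefore see two p-values for one question, the weaker being the one next to the event counts, with no rule on which governs.

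Second, seven coefficients estimated from a handful of events give widely scattered hazard ratios. Chance alone will often put a striking adjusted value in the table, and nothing in the section tells the reader to discount it.

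**Working it through.** **Inputs from the documents.** N = 32 (12 + 20; protocol 11.3, and SAP 3.1 for the analysed set). Exact enumeration gives the Simon optimal design for 0.5 v 0.7, one-sided 0.10 and 80% power as 12 then 20, so N reproduces. (Only N is used here; the response cut-offs are a separate matter.) No event number, power or precision is stated for the prognostic section. The first patient entered on 24 January 2019, the last is expected in 3Q 2020, and closure is two years after the last inclusion (synopsis; protocol 3.1). Potential follow-up is therefore about 24 to 44 months.

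**Step 1: ceiling on events per parameter.** Events per parameter = events / number of binary factors. With all 32 patients having an event: 32/7 = 4.6, 32/6 = 5.3, 32/5 = 6.4, 32/4 = 8.0. This needs no assumption on event counts. With an assumed 8, 12 or 16 events, the seven-factor model has 1.1, 1.7 or 2.3. SAP Table 26 has a missing-data row for PD-L1, so models that include it may use fewer than 32 patients.

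**Step 2: seven-factor fit against univariable fits on the same data.** Assumed: exponential event times; follow-up uniform on 24-44 months; independent null factors with prevalences 0.2 to 0.5 and at least 3 patients in the smaller group; event fractions 30%, 40%, 50% (mean 9.5, 12.8, 16.1 events); 4,000 datasets each.

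| | 30% | 40% | 50% |
|---|---|---|---|
| Any HR >4 or <1/4, seven-factor | 62.5% | 53.0% | 44.1% |
| Any HR >4 or <1/4, seven univariable | 31.7% | 23.6% | 16.7% |
| Type I error per coefficient, seven-factor | 6.3% | 7.6% | 8.5% |
| Type I error per coefficient, univariable | 3.0% | 3.8% | 4.3% |
| Non-convergence, seven-factor | 26.4% | 11.3% | 4.2% |
| Non-convergence, any univariable | 25.3% | 11.0% | 4.0% |

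Extreme-HR rates are among datasets where all fits converge; the ratios are 62.5/31.7 = 2.0, 53.0/23.6 = 2.2 and 44.1/16.7 = 2.6. For six factors the rates are 52.3, 43.3 and 35.4% against 27.8, 21.3 and 15.1%. For five factors they are 41.3, 33.5 and 26.1% against 24.1, 18.0 and 13.4%, with type I error of 4.9, 5.9 and 6.6%.

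**Step 3: count tests against log-rank.** Same follow-up; two-sided 5%; reference-group event fraction 25%, 35%, 50%; uncorrected Pearson; 20,000 simulations. Power at HR 3, Fisher / Pearson / log-rank (%):

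| Group sizes | 25% | 35% | 50% |
|---|---|---|---|
| 16 v 16 | 32.6 / 48.0 / 48.2 | 42.7 / 58.3 / 60.4 | 47.7 / 66.6 / 72.0 |
| 22 v 10 | 34.2 / 46.4 / 48.6 | 39.2 / 53.8 / 58.8 | 46.4 / 52.8 / 68.8 |
| 27 v 5 | 23.4 / 35.3 / 40.3 | 26.0 / 34.3 / 47.8 | 17.8 / 33.7 / 55.0 |

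Under the null the rejection rates are Fisher 1.6-3.0%, Pearson 4.3-5.8% and log-rank 4.8-6.0%. Fisher is conservative and Pearson is not. Much of Fisher's loss in balanced groups is conservatism: Pearson ignores time as well, yet stays within 0.2 to 5.4 points of log-rank there. Ignoring time costs more when groups are unequal and events are common.

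**The case against.** **Adjustment is tested only where it cannot help.** This stands. The simulations in step 2 contain no confounding. In a second set with overlap (assumed ECOG HR 3, clearance HR 2, latent correlation 0.4 among T stage, ECOG and clearance), a true T-stage HR of 3 has median 3.8-4.4 univariable and 3.8-4.7 with seven factors. When T stage has no effect given the others, the univariable median is 1.6 and rejects in 11-14%, against about 1.0 and 8-10% with seven factors. Overlap is a live matter. The SAP crosses creatinine clearance with ECOG (Tables 125-126, 150-151, 174-175). Protocol 4.1 allows clearance to be calculated by an age-dependent formula, measured, "or by 24-hour urine collection for determination of creatinine clearance". A reader might infer that every adjusted model should go, or that univariable estimates are more accurate. The documents give neither event counts nor factor overlap, so neither follows. The five-factor type I error, near 5%, also argues against condemning Table 127 outright.

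**Much of the false-positive rate is ordinary multiplicity.** Also true. Any p < 0.05 occurs in 30.3, 35.7 and 40.1% of seven-factor fits, while seven independent 5% tests give 1 - 0.95^7 = 30.2%. Removing adjustment would not cure that. Non-convergence cannot be charged to the multivariable model either, since it is shared.

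**A log-rank p-value duplicates the Cox Wald p-value.** Partly. Time-based p-values are already planned for every factor, so a reader should not infer that the SAP lacks them. The figure contents are not shown, and a log-rank p-value may be printed there. Footnotes are not tied to rows, so Pearson may be the test on the yes/no block in the six tables that list it. None of this is a reason to keep a weaker test that ignores time beside the event counts.

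**Conclusion.** The point holds as a minor one about secondary analyses.

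- The by-factor tables name only count tests for time-to-event outcomes. In the scenarios assumed, Fisher gives 18-48% power where log-rank gives 40-72%. Pearson's loss is small in balanced groups and up to about 21 points (55.0 - 33.7) at 27 v 5.
- The seven- and six-factor models cannot exceed 4.6 and 5.3 events per parameter. With roughly 10 to 16 events and null, independent factors, the seven-factor fit about doubles the chance of an extreme hazard ratio, or more, and type I error per coefficient is about 6-8.5%.

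The ceilings follow from N alone. The power, extreme-HR and type I figures rest on assumed event counts, prevalences and group sizes. A reader might also infer that the trial's main conclusion is at risk. It is not: the primary endpoint, the Simon decision and the planned Kaplan-Meier estimates use none of these models or tests.

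**What to change.** 1. In each by-factor EFS, PFS and OS table, replace the count-test p-value on the event yes/no block (for OS, the patient-status block) with a log-rank p-value. Print no p-value on the event-type block, which stays descriptive.
2. Present the univariable Cox columns and the existing univariate forest plots as the main prognostic result. Draw no prognostic conclusion from the seven- and six-factor columns of Tables 124, 149, 173 and 197. If an adjusted model is kept, limit it to a few factors named in advance, or use penalised fitting, and mark it as unstable. Whether to keep a reduced model such as Table 127 is the sponsor's choice.
3. Add: *These prognostic-factor analyses are exploratory; p-values are not adjusted for multiplicity.*

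The cost is SAP wording and changes to the table shells, with no new data. The downside is less emphasis on adjusted hazard ratios: overlap of creatinine clearance with ECOG and with age is then addressed only descriptively or in a small model. Multiplicity over seven factors and four endpoints, and sparse-cell non-convergence in univariable fits, remain, which is why the label is needed.

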### 11.3. Determination of sample size

The study will be conducted using a two-stage sequential design. Using the assumption that the treatment would be considered ineffective if it had a response proportion similar

to radiotherapy alone (P0: 0.5) but would be of considerable interest if it had a response proportion of 70% or more (P1: 0.7), the sample size requirement is 12 patients for the first stage and 20 additional patients for the second stage. Six or more responses in the first stage were required for continuation to second stage accrual, and 19 of a total of 32 patients treated to consider the study positive. The study was planned to have a type I error of 0.10 and a power of 80%.

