## 3. RESULTS

### 3.1. POPULATION AND RECRUITED PATIENTS

#### Analysis Population Definitions

All efficacy and safety analyses will be performed using the Safety population because all the patients (n = 32) fulfil the conditions to be included in the safety and efficacy (PP) populations, which include all patients who received at least 2 doses of Durvalumab and at least 3 weeks of radiotherapy.

Table 4: Populations and Hospital

(N=)	
Safety analysis set	Yes
Intention to treat population	Yes
Per protocol population	Yes
Hospital	

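### The Wald test named under four Cox tables carries no information for a factor level with no events, and is weak for a small level with one event

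*Combined protocol and SAP*

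**What the plan says.** Section 4 of the SAP's table of contents covers prognostic factors for four endpoints: EFS with bladder preservation, EFS (specific), PFS and OS. Each endpoint has a Cox table (Tables 124, 149, 173 and 197) with univariate and multivariate columns for age, sex, T stage, ECOG, non-invasive cancer history, PD-L1 and creatinine clearance, each at two levels. Each table prints the number of patients, events, HR, 95% CI and p-value, and each carries the footnote "HR = Hazard Ratio, CI = Confidence Interval; 2 Wald test". In the extracted text the marker 2 is not attached to any column, but no other test is named for the p-value column.

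A fifth Cox table, "Table 127: EFS bladder preservation multivariate model", defines only HR and CI and names no test.

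The analysis set is 32 patients, "because all the patients (n = 32) fulfil the conditions to be included in the safety and efficacy (PP) populations" (SAP section 3.1). Table 26 has a missing-data row for PD-L1, so models that include PD-L1 may use fewer.

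For the same factors and endpoints the SAP also compares event status by level, with footnotes such as "1. Fisher's Exact Test for Count Data" and in some tables Pearson's chi-squared. It adds Kaplan-Meier summaries, for example "Table 119: Median/mean EFS bladder preservation by PD-L1: High vs. Low/Negative (estimated by Kaplan-Meier". The text names no log-rank, likelihood-ratio, profile-likelihood or penalised method, and gives no significance level, event count or subgroup size for the Cox models.

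**The concern.** With 32 patients, one level of a two-level factor may hold few patients, and if that level does well it may have no events. A Wald test compares the estimated log hazard ratio with its standard error. When a level has no events, both run off to infinity and their ratio goes to zero. The table would then show a hazard ratio of about 0, an interval from 0 to infinity and a p-value near 1, so the strongest pattern the data can show reads as no evidence at all.

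The effect is lopsided. A factor that harms the smaller group produces events there and is tested normally. A factor that protects the smaller group is the one likely to be missed. At stake is how the prognostic-factor tables and forest plots are read.

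**Working it through.** **Inputs.** The protocol (section 11.3) plans "12 patients for the first stage and 20 additional patients for the second stage", that is 12 + 20 = 32, which agrees with n = 32 in the SAP. This is the only sample-size figure and it serves the primary endpoint; there is no power figure for the Cox models to reproduce. Protocol section 3.1 closes the study 2 years after the last inclusion. Everything else is assumed: two-sided 5% level, exponential times, subgroup sizes, event rates, and follow-up uniform over 24 to 44 months unless stated.

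**1. No events in one level.** For a binary factor x the log partial likelihood is the sum over events of xβ − log(n1·e^β + n0), where n1 and n0 are the numbers at risk in the two levels. If every event has x = 0, this rises without limit of argument as β → −∞, so there is no finite maximum. The information is the sum of p(1 − p), with p = n1·e^β/(n1·e^β + n0). It shrinks like e^β, so the SE grows like e^(−β/2) and z = β/SE goes to 0.

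- 16 v 16 patients, 0 v 10 events, one fitted data set: β = −28.7, SE = 451,736, Wald p = 0.99995, likelihood-ratio p = 0.00002.
- Same split, median over 200 draws of event times: Wald 0.999, score (log-rank) 0.0001, Fisher 0.0002.
- 8 v 24 patients, 0 v 10 events, median over 200 draws: Wald 0.998, score 0.041, Fisher 0.035.

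**2. One or two events.** Approximately, SE = √(1/d1 + 1/d0), where d1 and d0 are the event counts.

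- 1 v 10 events: SE = √1.1 = 1.049, so p < 0.05 needs HR below exp(−1.96 × 1.049) = 0.13.
- 2 v 10 events: SE = √0.6 = 0.775, so p < 0.05 needs HR below exp(−1.96 × 0.775) = 0.22.
- Fitted case, 16 v 16 with 1 v 10 events: β = −2.645, SE = 1.051, z = −2.52, p = 0.012.

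Given exactly one event in the better group and true HR 0.1 (follow-up 24 to 36 months), Wald is significant in 96% of runs at 16 v 16 and 65% at 8 v 24 when 40% of the reference group is event-free at 24 months. When 60% is event-free, the figures are 65% and 5%. So Wald usually works with one event, but not in a small level with few events overall.

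**3. How often a level has no events.** With 70% of the reference group event-free at 24 months, the hazard is −ln(0.7)/24 = 0.01486 per month; at HR 0.2 it is 0.00297. Averaged over the assumed follow-up, the chance that a patient has no event is [exp(−0.00297 × 24) − exp(−0.00297 × 44)]/(0.00297 × 20) = 0.904. All patients in the level escape with probability 0.904^8 = 0.45, 0.904^12 = 0.30 and 0.904^16 = 0.20.

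**4. Simulated power, univariate model, HR 0.2, 70% event-free.**

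| Split | No event in protected group (step 3) | Wald | Score | Fisher on counts |
|---|---|---|---|---|
| 8 v 24 | 45% | 0.5% | 25% | 25% |
| 12 v 20 | 30% | 7% | 41% | 36% |
| 16 v 16 | 20% | 22% | 53% | 37% |

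Firth's test is close to the score test (26% at 8 v 24). Repeat runs of 1,500 to 2,000 trials differ by a few points. At 16 v 16, strengthening the effect to HR 0.1 leaves Wald at about 20% while the score test rises to about 70%.

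**5. Range over event rates, HR 0.2, Wald v score.** With 60% event-free: 5% v 41% at 8 v 24, and 28% v 58% at 12 v 20. With 80% event-free: 0.4% v 23% at 12 v 20.

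**6. Harm and no effect.** At HR 3 in the smaller group (8 v 24, 70% event-free) Wald, score and Firth give 54%, 57% and 55%. With no effect, Wald rejects in 2–4% of trials, and score and Firth in about 4–6%.

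**The case against.** The plan does not rest on the Wald p-value alone. The Fisher and Pearson tests cover the same factors, endpoints and patients, and at 8 v 24 Fisher recovers essentially all the power that Wald loses. The Cox tables print event counts, and Kaplan-Meier results are planned by level, so a level without events would be visible. That much stands: a reader might infer that the SAP can hardly ever show a low-event subgroup to do better, and the documents do not support this. But the count tests ignore event times and censoring, recover less in balanced splits (37% v 53% at 16 v 16), and give no hazard ratio, interval or adjustment. In the 0 v 10 example the reader would see Fisher p = 0.0002 and Wald p = 0.999 for the same factor, with no rule on which to believe.

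Two other tempting readings also go too far. One is that Wald fails with any very small number of events; step 2 shows that it often works with one or two events in balanced groups. The other is that every Cox p-value in the SAP is a Wald test; Table 127 names none, and the footnote marker has no visible anchor.

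Finally, the stakes are modest. Protocol Table 8 plans only Kaplan-Meier estimation for the survival endpoints and lists no clinical factors for them. Even the better tests have limited power here, so a non-significant result would be inconclusive in any case.

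**Conclusion.** The point holds for Tables 124, 149, 173 and 197. For a level with no events, the Wald p-value and its matching interval are uninformative whatever the data; this is a mathematical fact and needs no assumption. For a small level with one event and few events overall, most of the power is lost. The sizes in steps 3 to 6 depend on assumed subgroup sizes, event rates and follow-up, none of which the documents give, and on a single-factor model. The same divergence can occur in the multivariate columns, but the loss there was not simulated.

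The response-rate endpoint and the Simon decision do not use these models and are untouched. This is a should-fix matter for the prognostic-factor results, not a threat to the trial's main conclusion.

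**What to change.** In Tables 124, 149, 173 and 197, report Firth-penalised Cox hazard ratios with profile-likelihood 95% intervals and p-values, and feed the univariate forest plots from the same fits. In the univariate columns the log-rank (score) p-value is an acceptable alternative. Apply the same method to Table 127 and name it there. Where a level has no events, print the penalised hazard ratio and its profile interval, not 0 with an unbounded Wald interval.

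An unpenalised likelihood-ratio test would also remove the zero-event failure, but it rejected in up to 8% of null trials in the smallest groups simulated, so the penalised version is preferable.

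The cost is one line in the SAP and a software option, with no new data. The downside is that penalised hazard ratios are pulled slightly towards 1.
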